6.4. Visit Windows

Visit window will not be used in the summarization or analysis of data.

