7.5. Criteria for Subject Study Discontinuation

A subject may elect to discontinue from the study at any time for safety or personal reasons. All subjects who discontinue from the study should complete the early study discontinuation procedures.

Any subject with a new positive response on questions 4 and/or 5 of the Columbia Suicide Severity Rating Scale (C-SSRS) will be immediately discontinued and evaluated for risk. Dosing may be restarted at the discretion of the Investigator following consultation with the Sponsor or its designee.

Subjects who discontinue early from the study will be evaluated for one of these primary reasons: AE(s), lost to follow-up, subject choice, inadequate therapeutic effect, and administrative/other. In addition to the primary reason, the subject may have indicated one or more of these reasons as secondary reasons for discontinuation. Study disposition information will be collected on the CRF.

Subjects who discontinue treatment for any reason, other than an SAE (even if the SAE is not treatment related) or an AE (unless the AE can be determined to be unrelated to treatment), may be replaced only after consultation with Sponsor or its designee.

Table 2:Schedule of Assessments

Assessment	Screening ^a	Baseline	Titra	ition	Т	freatmen	ıt	Completion/ Early Termination	7 Day Follow-up	14 Day Follow-up	30 day Follow-up*
Study Week	Up to -4	0	2*	4 ^g	6 ^g	8 ^g	10*	12 ^g	13/14 ^g	14/15 ^g	16/17
Study Days	Up to -28	0	14 + 3	28 + 3	42 + 3	56 + 3	70 + 3	84 + 3	7 Days Post Last Dose + 3	14 Days Post Last Dose + 3	30 Days Post Last Dose + 3
Study Visit Number	1	2	3	4	5	6	7	8	9	10	11
Informed Consent	Х										
Inclusion/ Exclusion	Х	Х									
Medical/Psychiatric/medicat ion History	Х	Х									
Randomization		Х									
Physical Exam/Vital Signs ^b	Х	Х		Х	Х	X		X	Х	Х	
ECG	Х	Х		Х	Х	Х		X	Х	Х	
Laboratory tests (Hematology and Chemistry) ^c	х	Х						Х	Х	X°	
Urine Drug Screen	Х	Х						X			
Urine Pregnancy Test	Х	Х						X		Х	
DSM-5 Criteria for TS	Х										
Yale Global Tic Severity Scale	Х	Х		Х	Х	Х		Х			
Clinical Global Impression - Tourette's Syndrome of Severity		Х		X	Х	X		Х			
Clinical Global Impression - Tourette's Syndrome of Improvement				X	X	X		Х			

Assessment	Screening ^a	Baseline	Titra	ition	Т	reatmen	ıt	Completion/ Early Termination	7 Day Follow-up	14 Day Follow-up	30 day Follow-up*
Study Week	Up to -4	0	2*	4 ^g	6 ^g	8 ^g	10*	12 ^g	13/14 ^g	14/15 ^g	16/17

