8.3. Subject Withdrawal, Removal, and Replacement Criteria

Any subject with a CDRS-R assessment indicative of the onset of a new depressive episode at any visit can be discontinued from study participation at the discretion of the Investigator. Any subject with a new positive response on questions 4 and/or 5 of the C-SSRS will be immediately discontinued and evaluated for risk. Dosing may be restarted at the discretion of the Investigator following consultation with the Sponsor or its designee.

The Investigator or subject may choose to stop study treatment at any time for safety or personal reasons.

Where possible, a subject who discontinues treatment will undergo protocol-specified end-of study procedures at the time of discontinuation. Date and reason(s) of premature discontinuation will be described in the CRF. In addition, the date of last dose of study treatment will be recorded on the Study Treatment Dosing CRF.

Subjects who discontinue treatment for any reason, other than an SAE (even if the SAE is not treatment related) or an AE (unless the AE can be determined to be unrelated to treatment), may be replaced only after consultation with Sponsor or its representative.

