4.1. Primary Efficacy Endpoint

The primary efficacy endpoint is the change in the Yale Global Tic Severity Scale – Total Tic Score (YGTSS-TTS, i.e., sum of the motor and phonic tic scores) from baseline (YGTSS-TTS score from Baseline visit) to end of therapy (YGTSS-TTS score from Week 12).

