4.1.1. Primary Efficacy Estimand

The mean change from baseline in the Yale Global Tic Severity Scale – Total Tic Score to end of therapy are compared between ecopipam and placebo for patients aged 6 to less than 18 years eligible for the trial.

The primary estimand is defined as the following:

Treatment: 4-week titration period followed by 8-week treatment phase with ecopipam HCI doses or matching placebo.

Target Population: all children and adolescent patients with Tourette's syndrome who were randomized, received at least one dose of study drug, and had at least one post Baseline scoring of the YGTSS (mITT population).

Variable: the change in the Yale Global Tic Severity Scale (YGTSS) from baseline to Week 12.

Intercurrent events: For the intercurrent events, receiving prohibited concomitant medication, change in dosing of allowed concomitant medication, and no dosing adjustment with BMI change, the treatment policy strategy will be used for the primary analysis, meaning the observed data at Week 12 will be used for the change from baseline in YGTSS. For the intercurrent event of study treatment discontinuation due to lack of efficacy and treatment related adverse events, for subjects with no YGTSS at Week 12, the hypothetical strategy will be used, meaning the non-collected data of YGTSS at Week 12 will be multiple imputed using similar subjects (relevant demographic/baseline characteristics) from the placebo arm. The intercurrent event 'death prior to Week 12' will be handled using the 'while alive and on-treatment strategy' using the last observed YGTSS assessment for the analysis of Week 12.

Population-level summary: treatment difference between ecopipam and placebo treatment groups using MMRM model in mITT population after having applied the hypothetical strategy and the while-on-treatment strategy, respectively, to the non-collected / non-observed Week 12 YGTSS assessments specified above.

The primary efficacy analysis approach is in line with the primary estimand. Potential confounders will be identified and sensitivity and/or supplementary analysis may be used to deal with missing data and assess the robustness of conclusions.

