6.1. General Methods

All analyses and outputs will be produced using SAS[®] version 9.4 or later. Unless otherwise specified, efficacy and safety summaries will be presented for each treatment. All other summaries will be presented for each treatment and overall. Continuous variables will be summarized using the number of observations (n), mean, standard deviation (SD), median, minimum, and maximum. Categorical variables will be summarized using number of observations (n), frequency, and percentages of subjects.

All relevant subject data will be included in listings. All randomized subjects entered into the database will be included in subject data listings. All by visit summaries will use the nominal visit. Unscheduled visits will not be summarized but will be included in the listings.

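### The SAP has no rule for assigning early-termination YGTSS scores to a visit; read literally, a score taken at dropout would enter as the Week 12 primary endpoint, against the plan's own estimand and sensitivity analyses

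*SAP*

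**What the plan says.** - **Schedule (protocol 7.5, Table 2; repeated in SAP 14.1).** A single column joins completion and "Early Termination". It is labelled Week 12, Day 84 ±3, Visit 8, and the YGTSS is marked in it. There is no separate ET column.
- **Timing (protocol 8.3).** Where possible, "a subject who discontinues treatment will undergo protocol-specified end-of study procedures at the time of discontinuation". Protocol 10.5 has subjects who cannot tolerate titration leave the study, so some of these visits can fall in the first four weeks.
- **Visit assignment (SAP 6.1 and 6.4).** "All by visit summaries will use the nominal visit"; "Unscheduled visits will not be summarized but will be included in the listings"; and "Visit window will not be used in the summarization or analysis of data".
- **Primary endpoint (SAP 4.1).** Change from baseline "to end of therapy (YGTSS-TTS score from Week 12").
- **Estimand (SAP 4.1.1).** After discontinuation for lack of efficacy or a treatment-related adverse event, "for subjects with no YGTSS at Week 12, the hypothetical strategy will be used", with imputation from similar placebo subjects. For death before Week 12 the rule is different: "using the last observed YGTSS assessment for the analysis of Week 12".
- **Sensitivity analyses (SAP 8.1.2, 14.4, 14.5).** Jump-to-reference imputes absent Week 12 scores as if the subject had followed the placebo course after dropout. The tipping-point analysis shifts the first value missing after dropout.

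**The concern.** An ET score taken on, say, Day 20 has only one scheduled label available, Visit 8/Week 12, and SAP 6.4 excludes reassigning it by study day. If the label is followed, that subject has a Week 12 value. Three things follow.

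1. The primary contrast becomes a mixed-time, last-observation-type comparison for dropouts who attend an ET visit. A Week 3 score also falls inside the four-week titration period and says nothing about the eight-week treatment phase.
2. The estimand's placebo-based imputation is switched off for these subjects, because its condition is that Week 12 is absent.
3. The jump-to-reference and tipping-point analyses lose these subjects' Week 12 values as something to act on, so they could look more reassuring than they should.

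The same Week 12 model estimate also feeds the interim conditional power in SAP 11.

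**Working it through.** **Step 1. Trace one record.** Take an ecopipam subject who stops on Day 20 and attends an ET visit that day.

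| Visit | Window (±3 days) | Value under the literal reading |
|---|---|---|
| Week 4 | Days 25–31 | missing |
| Week 6 | Days 39–45 | missing |
| Week 8 | Days 53–59 | missing |
| Week 12 | Days 81–87 | ET score from Day 20 |

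- SAP 4.1.1: Week 12 is present, so the imputation for discontinuation does not apply.
- SAP 14.4: the code uses a monotone method on Weeks 4, 6, 8 and 12, with no prior step to make the data monotone. Three missing values followed by an observed one is a non-monotone pattern, which that code does not handle.
- SAP 8.1.2.1 and 14.5: the shift is applied at the first missing visit and reaches later visits only by conditioning their imputed values. A Week 12 cell that is already filled is not imputed.

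**Step 2. Reproduce the plan's power.** Inputs from SAP 3.5: 75 per arm, difference 3, SD 6.1, alpha 0.05, dropout 10%. The test is two-sided (SAP 11). Normal approximation: power = Φ(δ / (σ√(2/n)) − 1.96).

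- n = 75 × 0.90 = 67.5 per arm. Standard error = 6.1 × √(2/67.5) = 1.050. 3/1.050 = 2.857. Φ(2.857 − 1.96) = 81.5%. A noncentral t calculation at n = 67 gives 80.7%. The stated figure of more than 80% reproduces.
- 80% power needs 65 evaluable subjects per arm; 65/0.90 rounds up to 73, close to the planned 75.

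**Step 3. Use ET scores as Week 12.** Let d be the dropout rate, equal in both arms, and f the share of the Week 12 treatment effect already present in an ET score. The documents do not give f, so it is shown as a range. Assume all dropouts attend ET, which gives the largest change. Then n = 75 and the expected difference is 3 × (1 − d + d·f). The standard error is 6.1 × √(2/75) = 0.996.

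| d | f | Expected difference | Power, ET used as Week 12 | Power, ET excluded |
|---|---|---|---|---|
| 10% (planned) | 0 | 2.70 | 77.4% | 81.5% |
| 10% | 0.25 | 2.78 | 79.6% | 81.5% |
| 10% | 0.5 | 2.85 | 81.6% | 81.5% |
| 10% | 1 | 3.00 | 85.4% | 81.5% |
| 20% (assumed) | 0 | 2.40 | 67.3% | 76.8% |
| 20% | 0.5 | 2.70 | 77.4% | 76.8% |

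Example: d = 10%, f = 0 gives 3 × 0.90 = 2.70; 2.70/0.996 = 2.71; Φ(2.71 − 1.96) = 77.4%.

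**Step 4. Break-even.** The two powers are equal when 1 − d + d·f = √(1 − d). At d = 10%, √0.90 = 0.949, so f = (0.949 − 0.90)/0.10 = 0.49. Below about half the effect, using ET scores costs power; above it, power rises.

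These are two-sample comparisons of Week 12 means, not the planned MMRM, so they indicate scale only.

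**The case against.** **No sentence makes an ET score the Week 12 value.** The nominal-visit sentence concerns by-visit summaries, and the documents do not show how the eCRF labels an ET record. Several passages point the other way. Jump-to-reference and the tipping point presuppose that dropouts lack later scores, the 14.4 code suits monotone dropout, and only the death rule openly moves an earlier score to Week 12. This stands: a reader might infer that dropout scores are definitely analysed as Week 12, and the documents do not go that far. It does not close the gap. SAP 6.4 bars windows in analysis as well as summaries. Treating ET records as unscheduled is not stated either, and would admit a subject to the mITT set on one score (SAP 5.3) with no value at a modelled visit.

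**The sensitivity analyses would still have data to impute.** A reader might infer that almost nothing would remain. ET attendance is only where possible, loss to follow-up is a listed discontinuation reason (protocol 7.5), and early dropouts would still lack intermediate visits. No attendance rate is given. The supportable statement is that these analyses would act on less.

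**A large power loss is not shown.** With 15% dropout on drug and 5% on placebo, completer changes of 6.4 and 3.4 points and no change at ET, the difference would be 0.85 × 6.4 − 0.95 × 3.4 = 2.21, with power about 60%. No document supports that split; in the earlier paediatric crossover study, which had shorter treatment, 38 of 40 subjects completed (protocol 5.3.2). Using that study's placebo changes of 2.1 points at Day 16 and 3.4 at Day 30 (protocol 5.2.2.1), timing alone under the same split would shift the contrast by 0.10 × (3.4 − 2.1) = 0.13 points.

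**HbA1c is not part of the problem.** Collecting it at completion or early termination is the stated plan.

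**Conclusion.** The point holds as a conflict within the SAP. The shared visit label, the timing of ET procedures and the exclusion of windows together lead a literal reader to file an early score under Week 12. The estimand, the sensitivity analyses and their code suggest that the authors meant such subjects to be missing at Week 12. As written, who has a primary-endpoint value is left to a programming choice.

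The likely effect on power is modest and can go either way. At the planned dropout it runs from about four percentage points lost (f = 0) to about four gained (f = 1), assuming equal dropout across arms and full ET attendance. The reason to act is that the quantity estimated could change from a Week 12 effect to a mixed-time one without the plan saying so. It should be settled before unblinding.

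**What to change.** In SAP 6.4, replace the blanket exclusion of windows with a rule for Completion/ET efficacy records, assigned by actual study day:

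- Count the score as Week 12 only if taken within the protocol window (Day 84 ±3) and before taper starts.
- Count it as Week 4, 6 or 8 if taken within that visit's ±3-day window and no scheduled value exists.
- Otherwise list it only.
- Whenever it is not counted as Week 12, Week 12 is missing and is handled under SAP 4.1.1 and 8.1.2.

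Use the protocol windows rather than midpoints: the midpoint of Days 56 and 84 is Day 70, so a midpoint rule would count a Day 71 dropout score as Week 12. Show ET as a separate row in the by-visit safety-scale tables. State also whether a listed-only score still qualifies a subject for the mITT set (SAP 5.3) and counts in the any-time responder definitions (SAP 8.2.6 and 8.2.7).

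Cost: one SAP paragraph and one derivation from the assessment date, with no new data. The downside is slightly fewer Week 12 observations.

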6.5. Pooling of Centers

Analyses will not include study site as a factor in the model. Region (North America and Europe) will be included, so sites will not be pooled based on the number of subjects, but by region.

6.6. Subgroups

Subgroups to be analyzed for YGTSS, CGI-S and CGI-I, CaGI-C and C&A-GTS-QOL as below:

- Baseline Age Group (6-11 years, 12-17 years)
- Region: North America and Europe
- Gender: Male and Female
- Prior TS Treatment: Yes or No
- YGTSS TTS Baseline Score Group: > = mean, < mean
- YGTSS TTS Baseline Score Group: > 2 SD from mean, within 2 SD of mean
- Body Weight Group: > 100Kg.

7. Demographic, Other Baseline Characteristics and Medication

7.1. Subject Disposition and Withdrawals

Subject disposition will be presented for all subjects, which include the following:

- Number of subjects enrolled
- Number of screened and reason for screen failure
- Number (%) of subjects randomized

Among the randomized subjects, the following will be summarized

- Number (%) of subjects in the Safety Set
- Number (%) of subjects in the Modified Intent-to-Treat Set
- Number (%) of subjects in the Per-Protocol Set
- Number (%) of subjects who completed the study
- · Number (%) of subjects who discontinued study prematurely and their reason

A separate by-subject listing of subject disposition and withdrawal will also be provided. Subjects who screen failed will be listed along with the date and reason for the screen failure.

Randomized subjects not included in an analysis set and their reason for exclusion will be summarized and listed.

7.2. Demographic and Other Baseline Characteristics

Demographics and other baseline characteristics will be summarized for the Modified Intent-to-Treat Set by randomized treatment and overall. Summary statistics and by-subject listings will be provided.

Demographics and baseline characteristics will include age, sex, ethnicity, race, weight, height, body mass index (BMI).

Age at Study day 1 = (Study day 1 visit date - date of birth + 1) / 365.25 and truncated to complete years.

Height (in cm) = height (in inches) * 2.54

Weight (in kg) = weight (in lbs) * 0.4536

BMI (kg/m²) = Weight(kg)/[Height(m)²]

7.3. Medical History and Concomitant Diseases

A summary table of the number and percentage of subjects by medical history, system organ class (SOC) and preferred term will be produced from the Safety Set. Medical history will be sorted alphabetically by SOC and in descending order of subjects per preferred term within each SOC.

Medical history will be coded using the Medical Dictionary for Regulatory Activities (MedDRA) version 22.0 or higher.

A separate by-subject listing of medical history will also be provided.

7.4. Medication

All prior and concomitant medications will be summarized based on classification using the Anatomical Therapeutic Chemical (ATC) classification and preferred drug name from the World Health Organization Drug Dictionary, version Mar 2019, or later.

A separate by-subject listing of medications will also be provided.

7.4.1. Prior Medication

Prior medications are defined as medications entered in the eCRF that either start, or end before the first dose of study medication. Prior medications will be summarized by ATC level 2 and preferred drug name for the Safety Set.

Prior medications which continue after first dose of study medication will also be classified as a concomitant medication.

7.4.2. Concomitant Medication

Concomitant medications are defined as medication on the eCRF that are taken on or after or are ongoing at the start date of dosing. Concomitant medications will be summarized by ATC level 2 and preferred drug name for the Safety Set.

8. Efficacy

The mITT set will be used for the analysis of the efficacy endpoints.

8.1. Primary Efficacy Endpoint and Analysis

8.1.1. Primary Efficacy Analysis

The Yale Global Tic Severity Scale (YGTSS) is a clinician-completed rating scale used to quantify overall tic severity as well as specific subdomains of tic number, frequency, duration, intensity, and complexity. Each of these subdomains is scored, on a 5-point scale, separately for motor and vocal tics and then summed across both motor and vocal tics to yield a total tic score (TTS) ranging from 0 to 50. The YGTSS also provides for an overall impairment rating (0 = "none" to 50 = "severe"). The YGTSS has demonstrated acceptable internal consistency, good interrater reliability, and acceptable convergent and divergent validity.

YGTSS will be assessed at Screening, Baseline and at Weeks 4, 6, 8 and 12.

The primary efficacy endpoint for this trial will be the change from Baseline (score of YGTSS-TTS {i.e., sum of the motor and phonic tic scores} at Baseline) to end of therapy (score of YGTSS-TTS at Week 12). The analysis of primary efficacy endpoint will use the MITT set. Results for the PP set will also be provided.

Statistical analysis:

The primary endpoint will be analyzed with a Mixed Model for Repeated Measures (MMRM) model using the SAS MIXED procedure with REPEATED statement. The model will include fixed effects for treatment, visit, interaction between treatment and visit, region, age group (0 = children 6-11, 1 = adolescents 12-17) and covariate for baseline YGTSS-TTS.

If there is no sample size increase at the interim analysis, then a single MMRM based on all the data will be performed. However, if the sample size is increased from the planned (150) then two MMRM models will be performed and combined using the CHW (Cui-Hung-Wang) method, which controls the type 1 error, one MMRM model on the data from Stage 1 (the interim analysis data) and the second on data from Stage 2 (post-interim data). Information on treatment effect from the two stages will be combined in the weighted test-statistic:

$$T_{CHW} = \sqrt{\frac{n_1}{N}} T_1 + \sqrt{\frac{n_2}{N}} T_2$$

T_{CHW} will be compared to a standard Gaussian distribution to determine the level of statistical significance. Here n₁ is the **actual** number of subjects in Stage 1 (planned to be 75 subjects), n₂ is the **planned** number of Stage 2 subjects before any sample size increase (i.e., 150 minus the actual number in Stage 1), N is the sum of n₁ and n₂ (i.e., 150), and T₁ and T₂ are the t-statistics for treatment difference from MMRM models on data from, respectively, Stage 1 and Stage 2 data. At a given stage, the mean difference Δ_{e-p} (treatment effect of ecopipam versus placebo) can be estimated by the difference $\hat{\delta} = LSM_e - LSM_p$ in least squares (LS) means of change from baseline at Week 12 between the ecopipam and placebo treatment groups, respectively. The LSMEANS statement with COV option will report the estimated covariance of LS means, which can be used to derive the variance $v \hat{ar}(\hat{\delta})$ of the difference $\hat{\delta}$. The t-statistic T₁ or T₂ can then be calculated as:

$$T = \frac{\widehat{\delta}}{\sqrt{\widehat{var}(\widehat{\delta})}}$$

If the planned sample size is adjusted and the CHW method used to analyze the primary endpoint, the MMRM model and sensitivity analyses of the complete dataset as if the sample size had been planned from the beginning will be performed to provide complementary interpretation to the CHW analysis.

8.1.2. Sensitivity Analysis

The primary efficacy analysis on change in the YGTSS-TTS at week 12 is to use MMRM model using all observed data. This model is appropriate when data is missing at random (MAR). To assess the robustness of the primary efficacy analysis, the following additional sensitivity analyses for missing data will be included for the mITT set:

- 1. Missing at Random (MAR) predictive mean matching multiple imputation method
- 2. Missing Not at Random (MNAR) jump to reference multiple imputation method
- 3. Tipping point under MNAR assumption

Details of sensitivity analysis for missing data and the statistical model are explained below.

8.1.2.1. Sensitivity analyses for missing data

Sensitivity analyses for missing data includes MAR predictive mean matching multiple imputation method, MNAR jump to reference multiple imputation method, and MNAR tipping point analysis. Details for the sensitivity analysis for missing data are given below:

1) MAR predictive mean matching multiple imputation method

All missing data will be imputed for patients missing data at week 12 using the predictive mean matching multiple imputation method (Heitjan and Little 1991, Schenker and Taylor 1996) for a MAR data assumption using fully conditional specification (FCS) method. The imputation model will include age group at baseline, region, treatment arm, baseline YGTSS-TTS, and YGTSS-TTS at all visits up to week 12 where the YGTSS is scheduled to be collected. This imputation will be performed using the SAS MI procedure with fcs specification. The resulting complete, imputed datasets will each be analyzed using the same model as the primary analysis model, and the resulting statistics combined using methodology provided by Rubin (1987) and Little and Rubin (2002). The SAS code for the multiple imputation methodology is detailed in the Appendix (Section 14.3).

2) MNAR jump to reference multiple imputation method

Data will be imputed for patients missing data at week 12 using similar predictive mean matching multiple imputation method. Under a MNAR data assumption, patients will have their missing data at week 12 imputed as if they behaved like placebo treated patients after dropout. Only placebo patients with complete data will be included in the imputation model. The imputation models will include age group at baseline, region, baseline YGTSS-TTS score, and YGTSS-TTS scores at all visits up to week 12 where the YGTSS is scheduled to be collected. After obtaining complete data sets, the complete data sets will be used in the analysis. The resulting complete, imputed datasets will each be analyzed using the same model as the primary analysis model, and the resulting statistics combined using methodology provided by Rubin (1987) and Little and Rubin (2002). The SAS code for the multiple imputation methodology is detailed in the Appendix (Section 14.4).

3) Tipping point analysis:

In the event that statistical significance in favor of ecopipam is determined from the primary analysis, subjects in the ecopipam group with a missing YGTSS-TTS score (change from baseline) will be assigned successively more extreme values, whilst subjects in the placebo group with a missing YGTSS-TSS score (change from baseline) will be assigned successively less extreme values, to find the point at which statistical significance is lost (i.e. the 2-sided P-value becomes greater than 0.05)

Details for tipping point analysis are described below:

- a. For patients that completed the study, intermittent missing data are considered as MAR and will be imputed by predictive mean matching multiple imputation method (Heitjan and Little 1991, Schenker and Taylor 1996). The imputation model will include age group at baseline, region, treatment arm, baseline TTS score, and TTS scores at all visits up to the imputed visit where the TTS is scheduled to be collected.
- b. For patients who discontinued due to any reason, all missing data will be imputed using the same predictive mean matching multiple imputation method. The imputed values will be adjusted under MNAR assumption:
 - Patients randomized to ecopipam: the first missing value after patients dropout will be analyzed assuming the unobserved outcome is on average worsened by ō1 (where ō1 = 1 to 10 or estimated treatment effect, whichever is higher, in step of 1) compared to the patients who have no missing value;
 - Patients treated by placebo: the first missing value after patients dropout will be analyzed assuming the unobserved outcome is on average better by 52 (where 52 = 1 to 10 or estimated treatment effect, whichever is higher, in step of 1) compared to the patients who have no missing value;

The penalty or reward will not be applied to the values from later time points as these values are penalized or rewarded through condition on previous time points. For each combination of ($\overline{0}1$, $\overline{0}2$), 100 imputed datasets will be obtained.

c. The resulting complete, imputed datasets will each be analyzed using the same model as the primary analysis model, and the resulting statistics combined using methodology provided by Rubin (1987) and Little and Rubin (2002).

The complete multiple imputation methodology, along with SAS code, is detailed in Appendix (Section 14.5).

